The degree of residual ridge resorption is closely related to the time since tooth extraction in both maxilla and mandible(*Ulm C, et al.1992*). The reduction in width is usually greater than the loss in height, and bone resorption is significantly larger at the buccal than at the lingual side (*Lekovic V, et al.1997*).

According to the Osteology Consensus Group 2011, ridge preservation is a general term for interventions that aim to preserve the ridge volume within the envelope existing at the time of extraction(*Christoph HF, et al 2011*).

In order to reduce alveolar bone dimensional changes, several techniques aiming at enhancing the regeneration process in the extraction socket have been adopted. Such as filling the socket with autogenous bone grafts or bone substitutes, guided bone regeneration (GBR) with resorbable or non-resorbable barriers and the use of various bone promoting molecules such as enamel matrix derivatives, recombinant growth and differentiation factors and autologous platelet concentrates (*Darby I, et al. 2009, Horowitz R, et al. 2012*).

Statins (hydroxymethylglutaryl co-enzyme A reductase inhibitors) are a group of lipid-lowering drugs that are widely used to prevent cardiovascular events (*Sotiriou CG & Cheng JW. 2000*), they are used orally to treat hypercholesterolaemia and hyperlipidaemia with well documented safety profile (*Guthrie RM, 2006*).

Furthermore, statins have been reported to stimulate the expression of bone anabolic factors, such as vascular endothelial growth factor and BMP-2 (*Maeda T, et al. 2003*), and to promote osteoblast differentiation and mineralization. In addition, it has been suggested that statins directly affect osteoclasts through mechanisms analogous to those of bisphosphonates (*Staal A, et al. 2003, Maeda T, et al. 2004*).

Statins can also modify the inflammatory cascades through pleiotropic actions at multiple levels, such as changing inflammatory mediators, altering leukocyte-endothelial cell interaction, and reducing expression of major histocompatibility complex- II (*Terblanche M, et al. 2007*).

Among statin drugs; Atrovastatin (ATV) has been demonstrated to exhibit favorable effects in the treatment of bone remodeling disorders and bone fractures through the promotion of osteogenesis and the reduction of bone resorption (*Wang JW, et al. 2007*).

The successful use of ATV to promote bone formation in vivo depends on the local concentration and there have been continuous efforts to find an appropriate

delivery system (**Kishida Y, et al.1991**), which allow localization and retention of the molecule and providing a matrix for mesenchymal cell infiltration and a substrate for cell growth and differentiation with degradation rate that does not inhibit bone growth and prevent fibrous tissue formation or fibrous encapsulation of the carrier (**Elavarasu S, et al. 2012**).

However, the most important limitation of local delivery vehicles is that the main bulk of the delivery vehicle or its acidic degradation products could interfere with regenerating tissues (**Marzouk KM, et al. 2007**). In addition, tissue-implanted materials could be surface friendly to biofilm-forming bacteria (**Becker PL, et al. 1994**).

Plasma rich in growth factors is an autologous technology using calcium ions to activate growth factor delivery from the platelets and to develop a fibrin network with the aim of promoting tissue regeneration (**Anitua E, et al. 2007**). This 100% autologous preparation not only enhances tissue healing but also improves the clinical outcomes of various surgical procedures by minimizing complications like pain, inflammation and morbidity (**Anitua E, et al. 2013a**).However, PRGF act on already differentiated cells, such as preosteoblasts and osteoblasts; however, they do not exert any effects on the stem cells present in bone tissue, whose differentiation is regulated by bone morphogenetic proteins (**Anitua E, et al. 2013b**).

Despite the numerous studies describing the benefits of PRGF (**Nazaroglu I, et al. 2009, Rivera C, et al. 2013**) and Statins separately , (**Sato D, et al.2005, Nishimura K .2008**) there has been a lack of clinical investigation into the simultaneous use of these agents in socket augmentation. Therefore the main objective of this study is to evaluate socket bone dimensions and quality following the use of PRGF derived fibrin scaffold as a carrier for Atorvastatinin socket augmentation clinically and histomorphometrically.

Aim of the study

This study will be performed to:

Compare 8 weeks postextraction augmented sockets using Atorvastatin loaded in Plasma rich in growth factors derived fibrin scaffold (PRGF/ATV) versus direct application of Atorvastatin (ATV) gel using:

- 1) Histomorphometric analysis of bone quality.
- 2) Clinical measurements of dimensional changes after extraction.

Subjects and methods

Thirty patients will be selected from the outpatient clinic of Oral Medicine, Periodontology, and Oral Diagnosis department, Faculty of Dentistry, Ain Shams University

Inclusions criteria:

1. Healthy adult patients as evidenced by Burkett's oral medicine health history questionnaire.
2. Both sexes.
3. Age from 20 –50 years old.
4. Having at least one hopeless tooth indicated for extraction.
5. Patient should agree to sign a written consent after the nature of the study will be explained.

Exclusion criteria:

1. Smokers.
2. Pregnant and breast feeding females.
3. Prisoners and handicapped patients.

Patients met the eligibility criteria will be randomly allocated using sequentially numbered sealed envelopes into 3 treatment modalities groups:-

Group I (PRGF/ATV): Will include 10 patients undergoing single tooth extraction followed by socket fill with PRGF loaded with Atorvastatin then suturing the socket.

Group II (ATV): Will include 10 patients undergoing single tooth extraction followed by socket fill with Atrovastatin gel then suturing the socket.

Group IIIEmpty socket(control) : Will include 10 patients undergoing single tooth extraction then suturing the socket.

All patients will receive implants after taking the bone biopsy after 8 weeks for histomorphometric analysis.

This proposal will be reviewed by the research ethics committee, the procedure will be fully explained to the patients and they will sign an informed consent.

Surgical procedure and clinical measurements:

- 1- Patients will undergo atraumatic extraction under local anesthesia for the involved tooth, to preserve bone and soft tissue followed by socket curettage.
- 2- Prior to surgery baseline clinical measurements (bone height measured by periodontal probe and bone width by bone caliper) will be taken for the alveolar ridge.
- 3- Socket will be filled with one of the assigned augmentation modalities;

Preparation of PRGF/ATV :

9ml venous blood will be collected from the same patient from peripheral circulation. The blood will be deposited in 3.8% w/v sodium citrate 1:9v/v. Platelet-rich in growth factors will be separated by centrifugation at 580 g for 8 minutes at room temperature. After centrifugation blood will be separated into plasma and cells, fractionation of plasma into 3 fractions:

Platelet very rich in growth factors - F3

Plasma with growth factors -F2

Plasma poor with growth factors - F1

To produce the (PRGF)(F3) loaded with Atorvastatin we will obtain by carefully pipeting a 1ml fraction of plasma immediately above the red blood then mixed with a weighted amount of Atrovastatin powder to produce 1.2% (PRGF /ATV) formulation, then 10% calcium chloride (50 µL for each 1 ml plasma) will be added and incubated

for 20 minutes in 37 c to produce a semi-solid mass (*Anitua E, 2001*).

Preparation of 1.2% (ATV) gel:

Atrovastatin methylcellulose gel will be prepared, by adding the required amount of biocompatible solvent to an accurately weighed amount of methylcellulose heated to obtain a clear solution then a weighed amount of ATV will be added to the above

solution and dissolved completely to obtain a homogeneous phase of polymer with a concentration 1.2% as described by *Pradeep AR, et al. 2013*.

4- Socket will be sutured.

5-Postoperative medications will include (Amoxicillin 500 mg t.d.s, Flagyl 500 mg twice/day and antiseptic mouth wash for 1 week).

6- Post operative instruction will be given to the patient and Suture will be removed after 1-2 weeks post operatively

7- Patient will be instructed to avoid wearing any prosthetic restoration.

8-After 8 weeks patient will come for postoperative clinical measurements and for taking biopsy and implant placement.

Histological Examination :-

Bone Biopsy will be taken by a trephine bur and the implant will be inserted in the same visit , and correspond to a type 2 delay according to the International Team for Implantology classification (*Chen ST & Buser D.2008*).

10- All the biopsy specimens will be fixed in 10% buffered formalin and demineralized in 10% ethylenediamine tetra acidic acid solution. A 7- μm -thick longitudinal section, representing the central part of each core specimen, will be stained with hematoxylin and eosin (H&E) for histologic examination. The histologic section will be examined using a research light microscope, and photomicrographs will be taken with the attached digital camera.

11- Histomorphometric measurement of the tissue image will be performed using the image analysis software.

- Total area of newly regenerated tissue including the newly formed bone above the old basal bone within the obtained core and the adjacent soft tissue .

Statistical analysis:

All the clinical and histomorphometric data will be collected, tabulated and subjected to statistical analysis.

References

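### Root type is neither stratified nor modelled, so any effect it has on the 8-week histomorphometry costs precision; one stratum and one model term would recover most of the loss

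*Protocol*

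**What the plan says.** In the protocol's Subjects and methods section, the inclusion list asks for "Having at least one hopeless tooth indicated for extraction". None of the three exclusions concerns the tooth. Neither jaw nor number of roots is restricted; the background discusses ridge resorption "in both maxilla and mandible". The group descriptions specify one extraction per patient, for example "Will include 10 patients undergoing single tooth extraction followed by socket fill with PRGF loaded with Atorvastatin then suturing the socket". That limits how many teeth are extracted, not how many roots the tooth has.

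Patients are "randomly allocated using sequentially numbered sealed envelopes into 3 treatment modalities groups", 10 in each. No stratum or block is mentioned. That the list is unstratified is therefore read from silence.

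Histomorphometry is the first aim. It rests on one core per patient: "All patients will receive implants after taking the bone biopsy after 8 weeks for histomorphometric analysis". Under Histological Examination the measure is "Total area of newly regenerated tissue including the newly formed bone above the old basal bone within the obtained core" plus adjacent soft tissue, with no stated scaling to core or socket size. Before treatment only the ridge is measured: "baseline clinical measurements (bone height measured by periodontal probe and bone width by bone caliper) will be taken for the alveolar ridge".

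The SAP compares groups by one-way ANOVA with Tukey HSD at 0.05 and names no covariate or stratum term. It is written in the past tense.

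**The concern.** Molar and single-rooted sockets differ in size and shape, and an unscaled tissue area could plausibly depend on that. If it does, two things follow with 10 patients per arm. First, the spread between root types inflates the ANOVA error term even when the arms are balanced, so real treatment differences are harder to detect. Second, in the one allocation the trial actually gets, root type may fall unevenly and move a group contrast, and the plan has no term to take that out.

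The histomorphometric outcome is the most exposed. It has no pre-treatment value, so a change from baseline cannot absorb part of the difference between teeth as it might for ridge height and width. Root type, however, is known before treatment and could be used.

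**Working it through.** **What can be reproduced.** The plan's only sample-size figure is 30, and 3 × 10 = 30 checks. No power, effect size or SD is given, so nothing further can be reproduced.

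**Inputs from the documents.** Three arms of 10, one tooth each; one-way ANOVA and Tukey HSD; alpha 0.05.

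**Assumptions, not in the documents.** Between 6 and 15 of the 30 teeth are multi-rooted. The root-type effect *e* is 0.5, 1.0 or 1.5 SD, where SD is the spread within a root type. The treatment difference for the power illustration is 1.2 SD.

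**Step 1: chance imbalance.** Random allocation of K multi-rooted teeth to arms of 10 (200,000 draws per K):

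| K of 30 | Groups I and II differ by ≥4 | Some pair differs by ≥4 |
|---|---|---|
| 6 | 4.8% | 12.1% |
| 9 | 9.1% | 20.5% |
| 12 | 11.6% | 25.0% |
| 15 | 12.1% | 26.1% |

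**Step 2: shift in a realised contrast.** A gap of 4 teeth moves the difference in means by (4/10) × *e* = 0.2, 0.4 or 0.6 SD. The standard error of a pairwise difference is √(2/10) = 0.45 SD.

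**Step 3: type I error.** With no treatment effect, the ANOVA rejects in 4.9–5.1% of trials over all allocations, for K = 9, 12 and 15 and all three effects. Among allocations where some pair differs by 4 or more, it rejects in about 6%, 9% and 12% for *e* = 0.5, 1.0 and 1.5.

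**Step 4: power without the factor.** With p the multi-rooted proportion, the variance within an arm is 1 + p(1 − p)*e*². The Tukey critical value on the t scale is 3.506/√2 = 2.479 (27 df), and the noncentrality is 1.2/(√variance × 0.447).

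| *e* | Variance, p = 0.2 | Power | Variance, p = 0.5 | Power |
|---|---|---|---|---|
| 0.5 | 1.04 | 56.6% | 1.0625 | 55.6% |
| 1.0 | 1.16 | 51.3% | 1.25 | 47.9% |
| 1.5 | 1.36 | 44.2% | 1.5625 | 38.5% |

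Direct simulation of the unstratified allocation agrees to within a point (43.5% in place of 44.2%).

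**Step 5: power with the factor.** With root type balanced by stratification, the residual variance returns to 1 on 26 df. The critical value is 3.514/√2 = 2.485 and the noncentrality 1.2/0.447 = 2.68, giving 58.4% whatever *e* is. With the factor in the model but unstratified allocation, simulation gives about 56–57%.

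**Step 6: if root type does not matter.** At *e* = 0, power without the factor is 58.5%. The factor under unstratified allocation gives about 56.6%, a loss of about 2 points. With balanced strata the loss is about 0.1 point (58.5% to 58.4%).

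**The case against.** The strongest reply is that randomisation already deals with this. Chance imbalance is part of the error that the ANOVA allows for, and broad eligibility with simple randomisation is a legitimate choice in a 30-patient study. Step 3 supports this: over all allocations there is no excess of false positives. A reader might infer that uneven root type biases the histomorphometric comparison or invalidates the ANOVA. The documents do not support that. The 6–12% rates arise only after conditioning on an unlucky allocation.

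A reader might also infer that histomorphometry cannot be adjusted because it has no baseline value. That is too strong. Root type is known before treatment, and baseline ridge height and width are measured; any of these could enter the model.

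It is also fair to say that the effect is assumed. Neither document says that root number affects new tissue in an 8-week core. At 0.5 SD the gain is between nothing and about 3 points. An even split of teeth is the least favourable case, which is why the range down to 6 of 30 is shown.

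What stands is narrower. The plan leaves a known pre-treatment source of variation out of both allocation and model. If its effect is 1 SD or more, the cost is material and cheaply avoided.

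**Conclusion.** The point holds as a cheap gain in precision, not as a flaw that undermines the trial. Against about 58% power with stratification plus the factor, the planned ANOVA loses about 2–3 points if the root-type effect is 0.5 SD, 7–10 points at 1.0 SD and 14–20 points at 1.5 SD. Adding the factor alone recovers most of this at 1.0 SD or more and little or nothing at 0.5 SD. These sizes rest on the assumed effect, the assumed 20–50% of multi-rooted teeth and a 1.2 SD treatment difference, none of which the documents give. The absence of stratification is inferred from silence.

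**What to change.** If enrolment has not started, the protocol's allocation paragraph should require the study tooth and its root type to be named and recorded before the envelope is opened. Entry allows more than one eligible tooth, and no rule says which is studied. Use two envelope series, single-rooted and multi-rooted, each in permuted blocks of 3 and 6 in random order. One binary stratum is as much as 10 per arm can reasonably carry, so jaw should be recorded but not stratified.

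In the SAP, add root type as a second factor beside arm for the histomorphometric and clinical outcomes, with Tukey comparisons on the adjusted means. Report root type by arm.

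If enrolment is complete, make only the SAP change, and make it before outcome data are seen. If analysis has begun, as the SAP's past tense may suggest, keep the planned ANOVA and report the adjusted model beside it as a labelled post hoc sensitivity analysis. Both routes need root type to have been recorded or to be recoverable from dental records.

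The cost is a second envelope series, arm totals that may end slightly off 10, and one degree of freedom. Under the SAP-only change, about 1–2 points of power are lost if root type has no effect.

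### The histomorphometry has no described specimen coding or masked reading; coding containers, slides and images until readings are locked would cheaply reduce observer bias

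*Protocol*

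**What the plan says.** Under Histological Examination, item 10 has each trephine core fixed, demineralized and cut. One longitudinal section, "representing the central part of each core specimen, will be stained with hematoxylin and eosin", is then examined by light microscopy and photographed. Item 11 adds that "Histomorphometric measurement of the tissue image will be performed using the image analysis software". The quantity listed is the area of regenerated tissue, including new bone, lying over the pre-existing basal bone in the core.

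The ridge outcome is measured on the patient. Item 8 of the surgical procedure reads "After 8 weeks patient will come for postoperative clinical measurements and for taking biopsy and implant placement". The instruments named for baseline are a periodontal probe and a bone caliper.

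The arms differ in what goes into the socket:
- Group I receives plasma mixed with atorvastatin and incubated "for 20 minutes in 37 c to produce a semi-solid mass".
- Group II has extraction "followed by socket fill with Atrovastatin gel then suturing the socket".
- Group III: "Will include 10 patients undergoing single tooth extraction then suturing the socket".

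The only related safeguard is in the allocation sentence: "Patients met the eligibility criteria will be randomly allocated using sequentially numbered sealed envelopes into 3 treatment modalities groups".

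The SAP covers software, a normality test, one-way ANOVA, Tukey HSD, paired t tests and the 0.05 level. Neither the SAP nor the Arabic summary mentions masking, specimen coding or an independent reader.

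**The concern.** Sealed envelopes can conceal the next assignment until it is made. They do nothing to keep the assignment from the person who later measures the outcome. The operator sees a semi-solid mass, a gel or an empty socket, so at least one team member knows the arm. Nothing in the available text keeps that knowledge away from the microscope.

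The software computes an area, but no automated rule is described for choosing the section or for drawing the line between new tissue and old bone. Both steps leave room for judgement. Histomorphometry is the first of the two stated aims. With 10 patients per arm, a reader who leans even slightly one way in one arm could create or hide a difference, and no later analysis could separate that lean from a treatment effect.

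**Working it through.** **1. What the text provides at each step**

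| Step | Judgement involved | Safeguard described |
|---|---|---|
| Assignment | None by the reader | Numbered sealed envelopes |
| Socket fill | Operator sees the material | None; masking the operator is not practical |
| Taking the core at 8 weeks | Where the trephine is placed | None |
| Choosing the central section | Which section represents the core | None |
| Measuring the image | Boundary between new tissue and basal bone | None |
| 8-week height and width | Placing and reading hand instruments, if the baseline ones are reused | None |

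Coding containers, slides and images acts on the fourth and fifth rows. It does not reach the third or the sixth.

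**2. Illustration of size**

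The plan states no power, SD or reader error, so it has no figure to reproduce. The inputs from the documents are three arms of 10 (protocol, group definitions) and one-way ANOVA with Tukey HSD at 0.05 (SAP). The assumption is that there is no true difference and that the reader shifts the mean of one arm by d SD.

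- Error degrees of freedom: 30 − 3 = 27.
- ANOVA: critical F(2, 27) = 3.354; noncentrality = 10 × d² × 2/3.
- One Tukey pair involving the shifted arm: q = 3.506, so the equivalent t is 3.506/√2 = 2.479; noncentrality = d/√(2/10).

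| d (assumed) | ANOVA noncentrality | ANOVA rejects | Tukey noncentrality | Tukey pair rejects |
|---|---|---|---|---|
| 0 | 0 | 5.0% | 0 | 2.0% |
| 0.10 | 0.067 | 5.5% | 0.224 | 2.2% |
| 0.25 | 0.417 | 7.9% | 0.559 | 3.8% |
| 0.50 | 1.667 | 17.8% | 1.118 | 10.2% |

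Simulation with 400,000 trials per case agrees: ANOVA 5.5%, 7.8% and 17.8%.

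**3. Which contrast is exposed**

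The aim compares PRGF/ATV "versus direct application of Atorvastatin (ATV) gel". If the reader favoured both active arms equally over the empty socket, that contrast would stay at 2.0%, while each active arm against the empty socket would rise to 2.2%, 3.8% or 10.2%. The ANOVA figures would not change, because its noncentrality is the same whether one arm or two are shifted by d. The stated contrast is affected only if the reader treats the two active arms differently.

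**The case against.** The strongest reply is that the plan nowhere says readers are unmasked, and that software does the measuring. The first part stands. A reader might infer that allocation is known at the microscope; the documents do not support that, and show only that masking is not described in the text available here. The second part does not stand, because the section and the tissue boundary still have to be chosen.

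It can also be said that the magnitude rests on assumption alone. That stands. At 0.10 SD the effect is trivial and at 0.25 SD it is modest. Nothing in the documents supports 0.50 SD, and the main contrast is untouched if both active arms are favoured equally.

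Two further inferences are tempting and go too far. One is that coding specimens would protect both outcomes. It would not: the 8-week height and width are read on the patient, where no label can hide the arm from an examiner who knows it. The other is that coding would eliminate the histology risk. The person placing the trephine is not identified and may know the arm, so the siting of the core can remain unmasked.

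Finally, the SAP is written in the past tense, so the readings may already exist. The protocol is in the future tense, so this is not conclusive, but the fix has to allow for it.

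**Conclusion.** The point holds for the histomorphometry. The available text describes no coding, masked reader or reading lock, and the endpoint leaves judgement to whoever measures it. The plan as written therefore allows a person who knows the arm to produce the result for a stated aim. This is a worthwhile, inexpensive improvement; it is not evidence that the results are biased.

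The false-positive rates of 5.5%, 7.9% and 17.8% show only how the planned ANOVA would respond to assumed shifts of 0.10, 0.25 and 0.50 SD in one arm. They are not estimates for this trial. For the ridge measurements, the supportable request is disclosure of whether the examiner knew the allocation.

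**What to change.** Add to Histological Examination, items 10 and 11:

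> Biopsy containers, slides and images carry a study code only. Section selection and histomorphometry are completed and locked before the measurer has access to the allocation. An existing team member who does not measure holds the key.

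If the readings are already complete, re-read the stored photomicrographs under code. This masks the measurement but not the earlier choice of section, which should be acknowledged.

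For item 8 of the surgical procedure, state whether the examiner taking the 8-week height and width knew the allocation; if so, report it as a limitation.

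The cost is labels for about 30 cores with their slides and images, and the discipline of keeping the key apart from the measurer. No extra visit, procedure, patient or change of test is needed. The documents do not describe staffing, so the availability of a key holder among the existing team is an assumption.

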Statistical Analysis plan

The collected data was tabulated and analyzed using Statistical Package for Social Science (***SPSS 15.0 for windows; SPSS Inc, Chicago, IL, 2001***). First; the normality of distribution of parameters was evaluated by **One-Sample Kolmogrovo-smirnov test**. Data were expressed as **mean and standard deviation (SD)**. **One-Way ANOVA test was used** for comparison between more than two study group means. Pairwise multiple comparisons to test the difference between each pair of means was performed using **Tukey HSD test**, and yield a matrix where different asterisks indicate significantly different group means. **Paired t test** was used to compare changes within same group. For all tests, **P <0.05 was considered significant**.

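### Aim 1 is bone quality, but the only histomorphometric quantity listed is a total tissue area that takes in both new bone and soft tissue

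*Protocol*

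**What the plan says.** The protocol's introduction says that "the main objective of this study is to evaluate socket bone dimensions and quality". Item 1 under Aim of the study is "Histomorphometric analysis of bone quality"; item 2 is the clinical measurement of dimensional change. Subjects and methods says that patients receive implants "after taking the bone biopsy after 8 weeks for histomorphometric analysis".

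Under Histological Examination, "Bone Biopsy will be taken by a trephine bur"; no core diameter, core length or fixed measurement region is given. One longitudinal H&E section from the central part of each core is examined. Item 11 then says: "Histomorphometric measurement of the tissue image will be performed using the image analysis software". A single bullet follows: "Total area of newly regenerated tissue including the newly formed bone above the old basal bone within the obtained core and the adjacent soft tissue". It carries no unit, percentage or denominator.

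The protocol's Statistical analysis section says: "All the clinical and histomorphometric data will be collected, tabulated and subjected to statistical analysis". The Arabic summary adds only that the 8-week samples are analysed histologically under the microscope. The SAP applies one-way ANOVA "for comparison between more than two study group means", followed by Tukey HSD, and names no outcome variable.

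**The concern.** The listed measure does not match the aim. A total area that takes in bone and soft tissue together describes the quantity of tissue. Two sockets that healed with very different amounts of bone can receive the same score, and two with the same bone content can receive different scores because more or less tissue came out in the trephine.

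Histomorphometry is the stated reason for the 8-week biopsy, and quality is one of the two parts of the main objective. If the bullet is followed as written, the three-group comparison for aim 1 is made on a variable that does not isolate bone. If it is not followed literally, several bone-specific values can be taken from the same section, and nothing in either document fixes the choice before results are seen.

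**Working it through.** The documents give no histomorphometric result, effect size or SD, so there is no stated figure to reproduce. The check is a reading of item 11 plus simple area arithmetic.

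**Inputs from the documents.** Aim 1 is bone quality. One quantity is listed, a total area. One section is taken per core. There are 3 groups of 10 patients.

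**Assumed inputs, for illustration only.** Section width is 2 mm (range 2 to 3). Regenerated length is 8 mm (range 4 to 10). Bone share is 40% or 55% (range 30% to 60%).

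**Formulae.** Total area = width x length. New bone area = total area x bone share. Soft tissue area = total area − new bone area.

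**Step 1: same size, different bone.**
- 40% bone: total 2 x 8 = 16 mm²; new bone 16 x 0.40 = 6.4 mm².
- 55% bone: total 2 x 8 = 16 mm²; new bone 16 x 0.55 = 8.8 mm².

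The pooled score is 16 mm² for both, although the second core holds 8.8 / 6.4 = 1.375 times as much new bone.

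**Step 2: same bone share, different recovery.** At 40% bone:
- 6 mm recovered: total 12 mm², new bone 4.8 mm².
- 10 mm recovered: total 20 mm², new bone 8.0 mm².

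The pooled score differs by 20 / 12 = 1.67, that is 67%, with no difference in share. The absolute bone area differs by the same factor, so tracing bone alone does not remove the dependence on core size.

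**Step 3: range of the assumptions.**

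| Section (mm) | Total (mm²) | New bone at 30% (mm²) | New bone at 60% (mm²) |
|---|---|---|---|
| 2 x 4 | 8 | 2.4 | 4.8 |
| 2 x 6 | 12 | 3.6 | 7.2 |
| 2 x 8 | 16 | 4.8 | 9.6 |
| 3 x 4 | 12 | 3.6 | 7.2 |
| 3 x 6 | 18 | 5.4 | 10.8 |
| 3 x 8 | 24 | 7.2 | 14.4 |

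In every row the total is the same for 30% and 60% bone. At a fixed share it runs from 8 to 24 mm² on section size alone.

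**Step 4: separate tracing.** Take the 8 mm core with 40% bone: 6.4 mm² of bone and 16 − 6.4 = 9.6 mm² of soft tissue. It could be reported as 6.4 mm², as 6.4 / 16 = 40% of the total, or as 6.4 / 9.6 = 67% of the soft tissue. Item 11 does not say that components are recorded, and neither document says which of these values would be compared.

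**Step 5: soft tissue as a location only.** If the closing words of the bullet merely say where the tissue lies, the quantity is still one total area and Steps 1 to 3 apply unchanged.

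**The case against.** The strongest reply is that item 11 can be read as recording new bone and soft tissue separately. New bone area is then itself a bone-specific outcome, and a share follows by division from the same section and software. This stands in part. A reader might infer from the bullet that aim 1 has no usable outcome on any reading. The documents do not support that: under separate tracing the outcome is under-specified, not absent. What remains is that the text does not describe separate tracing and does not choose among the values it would yield.

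A second reply is that the documents never equate bone quality with bone share. That is correct, and the absence of one particular ratio is not in itself an error. But a pooled total is not specific to bone, so the mismatch with a bone aim does not depend on share being the right definition.

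Third, the SAP names no variable of any kind, clinical or histomorphometric, so its silence is general and does not count specially against aim 1. That also stands. The difference lies in the protocol, which identifies the clinical measures (bone height by probe, bone width by caliper) but gives nothing equivalent and bone-specific for histology.

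Finally, the areas above rest on assumed core sizes and shares, and the equal totals follow from the definition. They show how the measure behaves; they do not estimate an error in this trial. That the area is absolute is also inferred from the wording, since no unit is printed.

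**Conclusion.** The concern holds in this form: on its plain reading, the only quantity listed for aim 1 is a pooled tissue area, which does not measure bone quality. A bone-specific value is obtainable from the same section, but it is neither described nor selected in the protocol or SAP.

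The size can only be illustrated. Under the assumed 2 x 8 mm section, a difference between 40% and 55% bone (6.4 against 8.8 mm²) gives no difference in the listed measure. At an equal 40% share, 6 and 10 mm of recovered tissue give a 67% difference. That the pooled area is blind to bone share does not depend on the assumed dimensions; the figures do.

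This is more than missing detail, because following the bullet literally gives a measure that does not serve the aim. The point is confined to the histomorphometric outcome. The clinical height and width measurements and the descriptive H&E examination are not affected.

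**What to change.** Replace the bullet in item 11 with text to this effect: on the same H&E section, new bone area and total regenerated tissue area are outlined separately; the total is all tissue, new bone plus soft tissue, in the core section above the old basal bone; the outcome for aim 1 is % new bone = new bone area / that total x 100; both absolute areas are reported beside it. Add a sentence on how the old basal bone boundary is identified, since both outlines depend on it.

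In the SAP, name % new bone as the histomorphometric variable for the one-way ANOVA and Tukey comparison. If the sponsor means something other than bone share by bone quality, it should name that bone-specific measure in the same two places.

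The cost is a few sentences in two documents and a second outline on up to 3 x 10 = 30 sections, with the same cores, stain and software. The SAP is written in the past tense; if the sections have already been measured, they need re-tracing and the change must be declared post hoc. A percentage alone does not show how much tissue regenerated, which is why the absolute areas stay beside it.
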